12.1.8.8 Serology

Serology screening will include human immunodeficiency virus (HIV) antibodies 1 and 2, hepatitis-B surface antigen (HBsAg), and hepatitis-C antibody (HCVAb).

12.1.8.9 Drug Screen

Urine drug screen will include amphetamines, barbiturates, benzodiazepines, cocaine, and opiates.

12.1.8.10 Pregnancy Screen

Samples for urine pregnancy testing (hCG) will be obtained.

Male patients of reproductive potential who are having intercourse with female partners of childbearing potential must agree to use 2 forms of contraception, 1 of which must be a barrier method, during the study and for 4 months after the last study drug administration. Acceptable barrier methods include a condom and diaphragm. Acceptable forms of birth control for female partners of childbearing potential are non-hormonal and hormonal intrauterine devices, hormonal birth control pills, hormonal birth control patches, hormonal birth control injections, hormonal birth control implants. Spermicide used alone is not an acceptable method and must be used with another acceptable form birth control method. Abstinence is acceptable if consistent with the patient's normal lifestyle.

Female patients are required to have negative hCG test results throughout the study. If a female patient becomes pregnant after she begins taking study drug, the procedures in [Section 12.2.2.7](#) should be followed.

In addition, for any reported case of delayed menstrual period (over 1 month between menstruations) and for those women with infrequent or irregular menstrual cycles, confirmation of absence of pregnancy should occur.

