8.3.2 Patient Completion

A patient will be considered to have completed the study when the patient has completed the Safety Follow-up visit that occurs 30 days (+ 4 day) after the Treatment Period 6 Day 0 visit. Enrolled patients who prematurely discontinue for any reason before completion of the study will be treated as outlined below in [Section 8.3.3.1](#).

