12.2.2.6 Laboratory and Diagnostic Abnormalities as Adverse Events

Clinically significant abnormal laboratory findings or other abnormal diagnostic assessments (e.g., ECGs, vital signs) that are detected in dosed patients or that significantly worsen relative to baseline in dosed patients will be reported as AEs. Clinical significance is based on the Investigator's judgment but will typically include findings that result in study withdrawal, result in active management of the patient, or are associated with clinical signs and symptoms. Since the study requires patients with elevated or abnormal sUA levels, abnormal sUA levels will typically not be an AE unless judged by the Investigator as being more severe than expected for the patient.

12.2.2.7 **Pregnancy**

While pregnancy itself is not considered to be an AE, any pregnancy complication or elective termination of a pregnancy for medical reasons will be recorded as an AE and followed. The outcome of all pregnancies must be followed up and documented even if the patient is no longer a study patient.

The Investigator, or his/her designee, will collect pregnancy information on every female who becomes pregnant while enrolled in this study and on every female partner of a male patient who becomes pregnant while the male partner is enrolled in this study. The Investigator will report to the Sponsor or Sponsor's designee within 24 hours of learning of a patient's or female partner of a patient's pregnancy. In the case of a female partner of a male participant enrolled in the study becoming pregnant while the male patient is enrolled in this study, a separate pregnancy partner informed consent form will be completed by the patient's partner. The patient or female partner of a patient must also be followed to determine the outcome of the pregnancy. Information on the status of the mother and child will be forwarded to the Sponsor or Sponsor Designee, as appropriate. Follow-up on the child will be to the first well-child visit. Any premature termination of the pregnancy will be reported.

A spontaneous abortion or congenital abnormalities/birth defects will be considered SAEs and will be reported as such. Furthermore, any SAE occurring as a result of a post-study pregnancy and is considered reasonably related to the study drug by the Investigator, will be reported to the Sponsor.

12.2.3 **Reporting Adverse Events**

12.2.3.1 **Adverse Event Reporting Period**

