The study period during which AEs must be reported is from the time the patient is dosed until the 30 (\pm 1) days after the last infusion of study drug. During the Screening Phase (from time informed consent is signed up to the time of dosing) any clinically significant changes in the patient's health will be recorded in the patient's medical history and will not be considered as AEs.

Investigators are not obligated to actively seek AEs or SAEs in former study patients. However, if the Investigator learns of any SAE, including a death, at any time after a patient has been discharged from the study, and he/she considers the event reasonably related to the study drug, the Investigator should promptly notify the Sponsor.

12.2.3.2 **SAE Reporting Procedures**

On discovery, all SAEs should be immediately reported (latest within 24 hours of knowledge of the event) to PAREXEL Safety Services by:

Completing the SAE report form and faxing the documents to PAREXEL Safety Services, using the appropriate regional PAREXEL SAE fax numbers below:

NA (Billerica): [contact]

or

Completing the SAE report form and submitting it to PAREXEL Safety Services via email utilizing the address (es) below:

NA: [contact]

In the event that the site is unable to complete the SAE form to report the event within 24 hours of their knowledge of the event, the investigators may report the SAE over the telephone via the SAE answering service, and then provide the completed SAE form via fax or email. If questions arise regarding the reporting procedures or the specifics of the reporting of an event, sites may call utilizing the following numbers:

NA (Billerica): [contact]

The Investigator will complete the SAE form and provide all case information available at the time of the initial report. The investigator must include the following mandatory case information:

1. The patient identification number
2. The event description
3. The seriousness criteria
4. The Investigator's causality assessment

The reporting Investigator must send the written and signed SAE report by facsimile or email, within 24 hours of observing, notification of, or learning of the SAE to PAREXEL Safety Services as described above. Follow-up information regarding an SAE and the supporting data, including laboratory findings and discharge summaries, should be sent by facsimile or email to PAREXEL Safety Services within 24 hours of receipt of the information.

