Appendix A Schedule of Assessments, continued

Assessment	Scr. - 45 d to D0 (Pre-dose) ³	Treatment Phase														EOS ¹	ET
		TP1 ²		TP2 ²		TP3 ²		TP4 ²		TP5 ²		TP6 ²					
Day	D0	D21	D0 ⁵	D21	D0 ⁵	D21	D0 ⁵	D21	D0 ⁵	D21	D0 ⁵	D7 ⁴	D14 ⁴	D21 ⁴	D28		
Tophus Assessment/Photography	X							X								X	X
Gout Flare Assessment ²²	X	X	X	X	X	X	X	X	X	X	X	X	X	X	X	X	X
Gout Flare Weekly Diary		Continuously on Weekly Basis ²³															X
Joint Assessment (tenderness, swelling)		X						X								X	X
Health Questionnaires ²⁴		X						X								X	X
Collect Sample for sUA	X	Refer to Schedule of Assessments (Appendix B) for sUA Sample Collection during Treatment Phase															X
PD/Uricase Activity Assessment		Refer to Schedule of Assessments (Appendix B) for PD/Uricase Activity Assessments during Treatment Phase															X
Study Drug Administration		Refer to Schedule of Assessments in Appendix B for Study Drug Administration during the Treatment Phase															
Infusion Reaction Follow-up		Refer to Section 12.2.1.5															
Concomitant Medications / Procedures		Continuously														X	X
AE Collection		Continuously														X	X
SAE Collection		Continuously														X	X

1. Phone call at 30 (+4) days after the last study drug infusion for assessment of concomitant medications/procedures, AEs, and SAEs.
2. Visit window at Day 21 of each Treatment Period is +2/-1 days; visit window at Day 7 and Day 14 of Treatment Period 6 is +2/-1 days; visit window at Day 28 of Treatment Period 6 is +3/-4 days.
3. Visit window is -2 days.
4. Assessments at this visit are permitted to be performed remotely (inclusive of collecting applicable lab draws and assessments per protocol visit windows).

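### Routine collection of partner pregnancies (12.2.2.7) ends about 86–93 days before the 4-month contraception window (12.1.8.10) for a man who receives all six doses

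*Protocol*

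**What the plan says.** Protocol 12.1.8.10 (Pregnancy Screen) asks men of reproductive potential with partners of childbearing potential to use two contraceptive methods, one of them a barrier, "during the study and for 4 months after the last study drug administration".

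Protocol 12.2.2.7 (Pregnancy) sets the collection rule. The investigator gathers pregnancy information "on every female partner of a male patient who becomes pregnant while the male partner is enrolled in this study". The partner consent form has the same limit: for a partner "becoming pregnant while the male patient is enrolled in this study, a separate pregnancy partner informed consent form will be completed".

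Four other provisions carry no enrolment limit:
- 12.2.2.7 requires the investigator to tell the sponsor within 24 hours of learning of a patient's or partner's pregnancy.
- 12.2.2.7 requires the outcome of every pregnancy to be followed, even after the patient has left the study.
- 12.2.2.7 classes spontaneous abortion and congenital abnormality as SAEs, and requires a report of "any SAE occurring as a result of a post-study pregnancy and is considered reasonably related to the study drug by the Investigator".
- 12.2.3.1 does not oblige investigators to look for events in former patients. However, "if the Investigator learns of any SAE, including a death, at any time after a patient has been discharged from the study" and thinks it related to study drug, the sponsor must be told.

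On the end of follow-up, 8.3.2 counts a patient as finished once he has "completed the Safety Follow-up visit that occurs 30 days (+ 4 day) after the Treatment Period 6 Day 0 visit". Appendix A, footnote 1, describes that contact: "Phone call at 30 (+4) days after the last study drug infusion for assessment of concomitant medications/procedures, AEs, and SAEs". It has no pregnancy item, and 12.2.2.7 says "While pregnancy itself is not considered to be an AE". Patients taken off study drug stay in visits to the end of Treatment Period 6 (7.1.3, 7.4.1.1).

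**The concern.** The two sections use different clocks. The contraception rule runs from the last dose. The collection rule runs with enrolment, which for a six-dose completer ends about a month after the last dose. The protocol thus treats four months after dosing as a time when conception should be avoided, but routinely collects partner pregnancies for only about the first quarter of it.

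Women may enter only if they are of non-childbearing potential (8.1), so partner pregnancy is nearly the only way this trial can produce reproductive-exposure data. After completion, the reports that arrive would mostly be those the site happens to hear of, or those judged serious and related. That is a selected set with no denominator. The partner consent form matters separately: as worded, a late pregnancy that the site does hear of has no form provided for it.

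**Working it through.** The documents give no figure for this gap, so there is nothing to reproduce. The check is date arithmetic.

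**Inputs**
- Contraception window: 4 months after the last dose (12.1.8.10). Over all start dates in 2021–2024, four calendar months last 120 to 123 days.
- End of enrolment for a six-dose completer: day 30 to 34 after dose 6 (8.3.2; Appendix A, footnote 1). The protocol defines when enrolment starts (consent) but not when it ends, so reading completion as the end is an inference.
- Men off drug who stay in visits: followed to Treatment Period 6 Day 28. With 28-day periods and no extension, that is 168 − 28 × (k − 1) days after dose k.

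**Gap = window − days from last dose to end of enrolment**

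| Situation | Days covered after last dose | Gap (days) |
|---|---|---|
| Six doses, completed | 30–34 | 120 − 34 = 86 to 123 − 30 = 93 |
| Off drug after dose 5, stays in visits | 56 | 120 − 56 = 64 to 123 − 56 = 67 |
| Off drug after dose 4 | 84 | 36 to 39 |
| Off drug after dose 3 | 112 | 8 to 11 |
| Off drug after dose 2 | 140 | none |
| Off drug after dose 1 | 168 | none |
| Lost 14 days after any dose (illustration) | 14 | 106 to 109 |

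For the six-dose completer the uncovered share is 86/120 = 72% to 93/123 = 76%. If a month were read as 28 days (112 in all), the gap would be 112 − 34 = 78 to 112 − 30 = 82 days.

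The plan expects about 8% to terminate early (13.1). On the SAP's 141 patients that is 141 × 0.08 = 11.3, of whom 94 × 0.08 = 7.5 on active drug.

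**Expected events, active arms**

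Responders stand in for six-dose men. This omits six-dose non-responders, who would add to the count. Response rates of 37% and 45% come from 13.1. The male share of 95.9% comes from study SEL-212/202 (7.6.3.2.2) and is assumed to carry over.
- Men: 94 × 0.37 × 0.959 = 33.4 to 94 × 0.45 × 0.959 = 40.6.
- With a partner of childbearing potential (assumed 10–50%): 3.34 to 20.3.
- Pregnancies in the gap (assumed 5–10% annual contraceptive failure): 3.34 × 0.05 × 86/365.25 = 0.04 to 20.3 × 0.10 × 93/365.25 = 0.52.

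The partner share and the failure rate do not come from the documents. Because 12.1.8.10 asks for two methods including a barrier, the failure rate may be lower.

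**The case against.** The strongest reply is that the sponsor has already dealt with post-study pregnancy. The 24-hour duty has no end date, outcomes are followed after a patient leaves, and related SAEs from later pregnancies are reportable. An investigator who learns of a late partner pregnancy could reasonably read the 24-hour duty as applying. Much of this stands. A reader might infer that every partner pregnancy after day 34 goes unreported, and the documents do not support that. What remains is narrower. The 24-hour sentence follows a collection sentence limited to enrolment, it works only if the site happens to hear, and nothing extends the partner consent form.

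A reader might also infer that men are never told to report late pregnancies. That cannot be concluded, because participant consent text and the Operations Manual are not available here and may contain such an instruction. Even so, the limits in 12.2.2.7 would still need changing.

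Nor does the gap apply to everyone. Men withdrawn from drug after dose 1 or 2 who stay in visits are covered for the whole window. Placebo completers have no exposure from this trial, although they may later enter the open-label extension.

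Finally, few events are expected and no endpoint, alpha or power is touched. That is correct, and it limits this to a low-cost safety improvement.

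**Conclusion.** The mismatch is real. For a six-dose completer, routine collection and the partner consent form stop about 86–93 days before the 4-month window ends. This rests on taking study completion (8.3.2) as the end of enrolment. The gap is smaller or absent for men taken off drug who stay in visits, and larger for those who withdraw consent or are lost soon after a dose.

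The documents support a gap in routine collection, in prompting and in partner consent. They do not support a claim that late partner pregnancies are wholly unreported. On assumed inputs, about 0.04–0.5 pregnancies would fall in the gap among active-arm responders. Efficacy conclusions are unaffected. The case for change is that the record is incomplete by rule over a period the sponsor itself set, and that correcting it costs very little.

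**What to change.** In both limited sentences of 12.2.2.7 (collection and partner consent form), replace the enrolment clause with: 'while the male patient is enrolled or within 4 months after his last dose of study drug, whichever ends later'.

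The last three words matter. Ending collection simply at 4 months after the last dose would remove cover that exists now: 168 − 123 = 45 to 168 − 120 = 48 days for a man stopped after dose 1, and 140 − 123 = 17 to 140 − 120 = 20 days after dose 2.

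At the End of Study call or Early Termination visit, in all arms, tell men with a partner of childbearing potential to report any pregnancy in that period. State that late reports go to the safety database only and do not delay study completion or database lock, since study end, unblinding and the primary analysis all wait on completed follow-up (7.5, 9.4.2, SAP 2.2).

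The cost is two clauses and one spoken instruction, with no new visit, sample or analysis. The downside is a few safety reports arriving after the study. Men already lost to follow-up will not hear the instruction. A separate phone call at 4 months is not needed.

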12.1.8.11 Definition of Childbearing Potential and Acceptable Contraceptive Methods

A woman is considered of childbearing potential (i.e., fertile), following menarche and until becoming post-menopausal unless permanently sterile. Permanent sterilization methods include hysterectomy, bilateral salpingectomy, and bilateral oophorectomy.

A postmenopausal state is defined as no menses for > 24 months without an alternative medical cause. A high follicle stimulating hormone (FSH) level in the postmenopausal range may be used to confirm a post-menopausal state in women not using hormonal contraception or hormonal replacement therapy.

However, in the absence of > 24 months of amenorrhea, one confirmatory FSH measurement must be obtained or documented.

For female partners of childbearing potential, the following methods of contraception, when used consistently and correctly, are considered reliable for participation of male patients in the study:

- Combined (estrogen and progestogen containing) hormonal contraception associated with inhibition of ovulation: oral, intravaginal, or transdermal
- Progestogen-only hormonal contraception associated with inhibition of ovulation: oral, injectable, or implantable
- Intrauterine device (IUD)
- Intrauterine hormone-releasing system (IUS)
- Bilateral tubal; occlusion
- Vasectomized partner (provided that partner is the sole sexual partner and that vasectomized partner has received medical assessment of the surgical success)
- Sexual abstinence (refraining from heterosexual intercourse during the entire study period; the reliability of sexual abstinence needs to be evaluated in relation to the duration of the clinical study and the preferred and usual lifestyle of the patient)

12.1.9 Premedication Regimen

Refer to [Section 10.6](#) for procedures about premedication regimens to prevent infusion associated reactions and gout flare.

12.2 Adverse and Serious Adverse Events

12.2.1 Definition of Adverse Events

Definitions in this section are in accordance with 21 CFR 312.32.

12.2.1.1 Adverse Event (AE)

An AE is any untoward medical occurrence associated with the use of a drug (i.e., study drug) in humans, whether or not considered drug related. An AE can therefore be any unfavorable and unintended sign (including an abnormal laboratory finding), symptom, or disease temporally associated with the use of a drug and does not imply any judgment about causality. An AE can arise with use of any drug or medicinal product. A treatment-emergent AE (TEAE) is an AE that starts or worsens at any time after initiation of study drug on Day 0 of Treatment Period 1 until the End of Study Visit (30 days after completion of the last dose of study drug).

Patients will be considered enrolled in the study upon signing the ICF. During the Screening Phase (from time informed consent is signed to immediately before dosing) any clinically significant changes in the patient's health will be recorded in the patient's medical history and will not be considered as AEs. AEs (and thus SAEs) will be collected from the time the patient is dosed (infusion is started) until the end of the End of Study Visit.

12.2.1.2 **Serious Adverse Event (SAE)**

An SAE is any AE that occurs irrespective of study treatment assignment, if it satisfies any of these criteria:

- Results in death;
- Is life-threatening;
- Requires inpatient hospitalization \geq 24 hours or prolongs existing hospitalization;
- Results in persistent or significant disability or incapacity or substantial disruption of the ability to conduct normal life functions;
- Is a congenital anomaly or birth defect;
- Is an important medical event that, based upon appropriate medical judgment, may jeopardize the patient or patient may require medical or surgical intervention to prevent one of the outcomes listed above.

12.2.1.3 **Suspected Adverse Reaction**

A suspected adverse reaction is an AE for which there is a reasonable possibility that the drug caused the AE. For the purposes of IND safety reporting, “reasonable possibility” means there is evidence to suggest a causal relationship between the drug and the AE. Suspected adverse reaction implies a lesser degree of certainty about causality than adverse reaction, which means any AE caused by a drug.

12.2.1.4 **Unexpected Adverse Events and Unexpected Suspected Drug Reaction**

An AE or suspected adverse reaction (an AE where there is a reasonable possibility that the drug caused the event; suspected drug related) is considered “unexpected” if it is not listed in the SEL-212 Investigator’s Brochure or is not listed at the specificity or severity that has been observed.

12.2.1.5 **Infusion Reactions / Adverse Events of Special Interest**

A study drug-related AE that occurs within 24 hours after initiation of study drug infusion will be assessed as an infusion reaction. An infusion reaction suspected to be anaphylaxis will be assessed according to the clinical criteria for the diagnosis of anaphylaxis based on the National Institute of Allergy and Infectious Diseases (NIAID) / Food Allergy & Anaphylaxis Network (FAAN) Symposium criteria. ([Sampson 2006](#)).

Infusion reactions will be managed and treated as described below. In addition to premedication with antihistamines and steroids ([Section 10.6.2](#)), the following steps will be implemented in this protocol to either reduce the risk of infusion reactions or manage infusion reactions.

- Patients with prior exposure to uricase therapy will be ineligible
- Patients with a history of anaphylaxis or severe allergic reactions, history of severe atopy, angioedema, or previous infusion reactions will be excluded from the trial.
- Study drug will be administered at controlled rates only in a healthcare setting and by healthcare providers sufficiently equipped and prepared to manage infusion reactions including anaphylaxis.

- In case of infusion reaction, sites will perform specific assessments as specified in the Study Operations Manual.
- Each patient will be observed for infusion reactions after dosing of study drug in the clinic for approximately 4.5 hours from the start of study drug infusion. Patients will be informed about the signs or symptoms of infusion reactions and will be instructed to notify the Investigator immediately if they believe they are experiencing a reaction.
- Each patient shall remain for a minimum of 1 hour after the completion of infusion of study drug for a period of safety observation.
- All patients will be contacted approximately 24 hours after infusion to determine whether any infusion reaction AEs occurred.
- Patients who experience an infusion reaction will be contacted approximately 24 hours after the event as follow-up.
- Only sites with immediate capability to appropriately respond to a reaction of this severity will be allowed to participate in the trial to reduce the risk to any patient.
- Infusion Reactions (an AESI) will be reported to Parexel Safety in the same manner as SAEs using the same form but ticking the AESI box rather than the SAE box.

Adverse events of special interest (AESI) will be recorded specifically for occurrences of: gout flares, infections, malignancies, viral infections, interstitial lung disease, stomatitis, infusion-related reactions including anaphylaxis, thrombosis (e.g., deep venous thrombosis, pulmonary embolism), and the following laboratory tests, if deemed clinically significant by the PI: hyperlipidemia, worsening of renal function tests, proteinuria, and leukopenia.

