7.1.1 Screening Phase

After providing written informed consent, the patient is considered enrolled in the study. Patients will be evaluated for inclusion during the Screening Phase. For all patients, the standard Screening Phase will be up to 45 days prior to Baseline. The Screening Phase may be initiated by a preliminary screening with an abbreviated informed consent focused on COVID-19 testing and serum uric acid levels followed by providing study-wide informed consent and the remainder of screening assessments if determined to proceed. **Of note**, if the sUA level obtained during preliminary screening meets eligibility requirements (i.e., ≥ 7 mg/dL), the sUA should **not** be repeated during the subsequent complete screening assessment. Concurrently with the Screening Phase, a premedication period for potential gout flare with colchicine (or non-steroidal anti-inflammatory drug [NSAID], if colchicine is contraindicated) of at least 7 days prior to Baseline will be required for all patients, and a washout period of at least 7 days will be required prior to Baseline for patients on any urate-lowering therapy (ULT). Both the ULT washout

period and the gout flare prophylaxis period may be started earlier than 7 days prior to Baseline. At the discretion of the PI, chronic refractory gout patients whose sUA is lower than the eligibility level of ≥ 7 mg/dL on prescreening or initial screen, may undergo ULT washout prior to retesting the sUA. Initiation of gout flare prophylaxis with colchicine (or non-steroidal anti-inflammatory drug [NSAID], if colchicine is contraindicated) can also be considered coincidentally with the ULT washout to prevent a potential gout flare.

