8.3 Patient Completion and Withdrawal Criteria

8.3.1 Screen Failures and Replaced Subjects

A patient is considered enrolled in the study at the time of ICF signature. Any patient that is screened but not dosed will be considered a screen failure and the reason for failure will be documented. Any patient that is randomized but not dosed will be replaced and not included in the ITT population, and the reason for not being dosed will be documented.

Within the 45-day screening window, out-of-range laboratory tests may be repeated up to 2 times before declaring a screen failure (except for COVID-19 testing as described in [Section 12.1.8.7](#)). After the 45-day screening window, patients can be re-screened once.

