### 8.3. Medical History

Medical history will be coded using current version of Medical Dictionary for Regulatory Activities (MedDRA®). Medical history will be listed for all randomized patients. No summaries will be provided.

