ii) Exposure –adjusted event rate in treatment group A based on events = Number of all events in treatment group A / Total sum of the treatment exposure time of all patients in treatment group A.

Listings of TEAEs and non-TEAEs will be provided.

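### AE and SAE collection starts only at the first infusion, so events during the protocol-imposed run-in are recorded as medical history, with no grading, causality assessment or expedited report

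*Protocol*

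**What the plan says.** Protocol 12.2.1.1 sets the start of collection: "AEs (and thus SAEs) will be collected from the time the patient is dosed (infusion is started". For the time from consent to dosing it says that "any clinically significant changes in the patient's health will be recorded in the patient's medical history and will not be considered as AEs". Protocol 12.2.2 repeats the medical-history rule. Protocol 12.2.3.1 restates both parts: "The study period during which AEs must be reported is from the time the patient is dosed", and earlier changes go to "medical history and will not be considered as AEs".

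In the same interval the protocol intervenes:
- Protocol 7.1.1 states that "a washout period of at least 7 days will be required prior to Baseline for patients on any urate-lowering therapy (ULT"; Protocol 10.5 sets the same minimum.
- Protocol 10.6.1 starts colchicine, or an NSAID where colchicine is contraindicated, at least 7 days before the first dose. Only patients with contraindications to both are exempt.
- Protocol 10.6.2 gives prednisone and fexofenadine before each dose, so the first of these precede the first infusion.

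Screening may last up to 45 days (7.1.1), and randomization may take place from Day -7 (Appendix A, footnote 15). Protocol 8.3.1 adds: "Any patient that is randomized but not dosed will be replaced and not included in the ITT population".

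On reporting, SAP 8.3 lists medical history for all randomized patients and adds "No summaries will be provided". SAP 8.4 summarizes gout flare assessments at screening and baseline. SAP 8.1 lists screen failures with the reason. SAP 10.3 says "Listings of TEAEs and non-TEAEs will be provided".

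**The concern.** A patient can be harmed by something the protocol requires before receiving any study drug. An example is a serious reaction to newly started prophylaxis. Protocol 12.2.2 encourages patients to report health changes from consent, so the site is likely to hear of such an event. Yet the rules then remove it from the safety system. It is not an AE, so it cannot be an SAE, and the 24-hour route in 12.2.3.2 does not apply.

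What is at stake is oversight of study-mandated procedures, not the comparison of SEL-212 with placebo. There is also an internal tension. Protocol 10.6.1 describes a prophylaxis regimen that begins before dosing and directs that flares be recorded as AEs, and 12.2.1.5 makes gout flare an AESI. Under 12.2.1.1, a flare that begins in the run-in cannot be an AE.

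**Working it through.** **Inputs.** Washout and prophylaxis minimum, 7 days (Protocol 10.5, 10.6.1). Screening maximum, 45 days (7.1.1). Six infusions 28 days apart, so the last is on day 5 × 28 = 140. Safety follow-up, 30 days after the last infusion (7.1). Planned number randomized, 140 (7.2); the SAP has 141.

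**1. Reproduce the plan's own duration.** Protocol 7.1 gives total participation as 184 to 215 days.
- Upper end: 45 + 140 + 30 = 215, as stated.
- Lower end: 184 − 140 − 30 = 14 pre-dose days. With the 7-day minimum the total would be 7 + 140 + 30 = 177.

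The stated range therefore corresponds to 14 to 45 pre-dose days, while the procedural minimum is 7.

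**2. Share of participation without AE collection.** 7/177 = 4.0%; 45/215 = 20.9%.

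**3. Patient-time for 140 patients, if all had the same window.**
- 140 × 7 = 980 patient-days (980/365.25 = 2.7 patient-years)
- 140 × 14 = 1,960 patient-days (5.4 patient-years)
- 140 × 45 = 6,300 patient-days (17.2 patient-years)

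With the SAP's 141 patients the ends are 987 and 6,345.

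**4. Follow one serious pre-dose event through the rules.**
- 12.2.1.1: it is medical history, not an AE.
- 12.2.1.2: an SAE is an AE that meets a seriousness criterion, so it is not an SAE.
- 12.2.2.2 and 12.2.2.3: causality and grading apply to AEs, and causality is asked for study drug only.
- 12.2.3.1: the only provision outside the reporting period covers SAEs learned of after discharge from the study and thought related to study drug.
- SAP 5.2 and 10: safety analyses use the Safety Set, which requires dosing.

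**5. What the reader of the study report would see.**
- Randomized and dosed: a line in the medical history listing; flare assessments at screening and baseline also appear in a summary.
- Randomized, not dosed: the patient is in neither the ITT nor the Safety Set. The patient remains in the Randomized Set used for listings, so medical history is still listed.
- Failed screening before randomization: only the reason for failure.

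**6. Effect of extending collection.** TEAEs would still start at first study drug (Protocol 12.2.1.1, SAP 10.3). TEAE tables, exposure-adjusted rates and sample size do not change.

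**The case against.** The strongest reply is that this is a deliberate rule, stated consistently in three places and tied to an AE definition based on study drug. The safety objective is SEL-212 compared with placebo. Washout, prophylaxis and premedication are common to all arms and are not the randomized contrast. Patients stay off ULT, prophylaxis continues and premedication is repeated before doses 2 to 6, all with AE collection running, so only events that begin before the first infusion are lost. What the DSMB sees is set by a charter outside these documents. All of this stands. It limits the point to oversight of the run-in but does not supply a reporting route.

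Three stronger readings are tempting, and the documents do not support them.

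- *Run-in events are never reported.* Medical history is recorded up to dosing (Protocol 12.1.1) and listed for randomized patients (SAP 8.3). Flare assessments are summarized (SAP 8.4), and so is the sUA change from screening to baseline (SAP 8.4, 8.6).
- *The SAP's non-TEAE listing contradicts the protocol because no such event can exist.* Non-TEAEs need not be pre-dose. The TEAE period ends 30 days after the last dose, but patients withdrawn from drug are followed to Day 168. After one dose that leaves 168 − 30 = 138 days, and Appendix A marks AE collection as continuous. Protocol 12.2.3.1 may close collection at 30 (±1) days, but that is a separate question. What is certain is only that pre-dose events cannot enter the listing.
- *The missed events can be counted from the flare rate in Protocol 5.4.* Seven flares a year over 7 to 45 days in 140 patients gives 7 × 7/365 × 140 = 18.8 to 7 × 45/365 × 140 = 120.8. This is a background rate, not harm from the run-in. The upper end applies the screening maximum to everyone, and flares are the one pre-dose event that the SAP does summarize.

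**Conclusion.** The point holds in this form: an event that begins between consent and first infusion, however serious and even if caused by a protocol-mandated step, is outside AE and SAE collection and has no expedited route. Apart from the flare assessments it is listed without summary, and for patients who fail screening before randomization only the reason for failure is listed.

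The size is 7 to 45 days per patient, or 980 to 6,300 patient-days for 140 patients, with up to 7 of those days after randomization. The 7-day end applies to patients on washout or prophylaxis. The 45-day end is the screening maximum, not the length of any one procedure. Patients screened but not randomized come on top and cannot be counted. The number of missed events cannot be computed, because the documents give no rates for washout, prophylaxis or premedication.

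This is a gap worth closing because closing it is cheap. It does not bias the comparison between arms.

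**What to change.** - In Protocol 12.2.1.1, 12.2.2, 12.2.3.1 and Appendix A, collect and report SAEs from informed consent. Collect AEs assessed as related to a protocol-mandated procedure (ULT washout, flare prophylaxis, infusion-reaction premedication) from the start of that procedure.
- Add a causality field for those procedures, since 12.2.2.2 covers study drug only.
- Leave the TEAE definition as it is.
- Reconcile the flare-recording instruction in 10.6.1 with the start of collection in 12.2.1.1.
- In SAP 10.3, present pre-dose events separately as non-treatment-emergent on the All Randomized Set, with a listing for screened patients who were not randomized.

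The cost is some extra SAE forms, one CRF field with site instruction, and one output; no added visits. An amendment at this stage (protocol version 7.1, December 2022) would not capture patients already screened prospectively. For them a partial remedy is available in the SAP alone: tabulate medical history entries with onset after consent on the All Randomized Set, provided onset dates were recorded.
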